American Indian/Alaska Native	1	1	2
Asian	5	5	10
Black/African-American	13	13	26
Hawaiian/Pacific Islander	1	0	1
White	73	71	144
Multirace	3	3	6
Other race	6	5	11
Ethnicity	Male (N)	Female (N)	Total (N)
Hispanic (Latino/Latina)	16	16	32
Non-Hispanic	83	85	168

Briefly describe study procedures. Include any local site restrictions, for example, “Subjects enrolled at Partners will not participate in the pharmacokinetic portion of the study.” Describe study endpoints.

Potential eligible participants will be directed to our study recruitment website (www.downsyndromeclinictoyou.com) to complete the eligibility screening questionnaire (Appendix A). Information of frequently asked questions and answers will also be provided on our study recruitment website (Appendix B). After a questionnaire is submitted and a parent/caregiver is deemed eligible, our study personnel will send an email notification containing a unique link to our online consent form in REDCap (Appendix C). Once they have provided consent, the parent/caregiver will continue on to complete the baseline assessment. Our study personnel will then be notified by e-mail, after which we will randomize the participant 1:1 to either the Intervention or Control arm (Appendix D).

To limit chance confounding between variables that might influence guideline compliance, we will stratify randomization based on two variables (six strata) collected prior to randomization during the Baseline assessment when data are gathered only from parents (PCPs are first surveyed after their appointment with the patient who has Down syndrome):

- Travel time to primary care physician: < 30 minutes; 30–60 minutes; > 60 minutes
- Primary insurance: public (e.g., Medicaid, Medicare) or private

Given the sequence of study procedures, we will not stratify on any variables reported by the PCP. With 200 participants randomized, we expect to

achieve effective mixing of PCP characteristics that might be associated with differential guideline compliance. Moreover, by not conditioning on PCP characteristics, findings from our primary analysis will be most broadly generalizable. However, we do want to increase precision in our secondary analyses by accounting for relevant sources of variation among PCP practices. To this extent, we will collect the following variables for inclusion as covariates:

- PCP practice size: < 5 MDs; 5–9 MDs; 10+ MDs (collected in PCP Experience Survey during Post-visit Assessment 1)

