guidance offered by the *Caregiver Checklist* and *Primary Care Provider Plan*, similar to the voluntary questionnaire used in our preliminary study described above. We also anticipate including open-text responses solicited from caregivers and providers about their experience using the system.

Data Analysis Plan

Our primary analysis will compare the mean number of caregiver-reported evaluations completed within 7 months of the index PCP visit between the intervention and usual care arms. We will analyze the data using a generalized linear model assuming beta-binomial distributed counts of evaluations among those indicated with parameters estimated by maximum likelihood. We will confirm our inference using a permutation test by direct randomization of assigned treatment labels. Significant benefit will be declared if the mean number of recommended tests is greater among participants randomized to the intervention and a two-tailed p-value for the treatment comparison is less than 0.05. A significant effect of the intervention will be declared only if the permutation test concurs with inference from the beta-binomial regression as the permutation test makes no assumptions concerning the true distribution of the data. We will analyze longitudinal changes in our secondary outcome measures using a shared-baseline repeated-measures ANOVA for each of 6 quality of life outcomes derived from the two PedsQL instruments. Linear contrasts will be used to test for treatment-specific improvements over time. As a sensitivity analysis, we will also use simple two-group Wilcoxon ranksum tests to compare changes from baseline in each follow-up assessment individually. With 6 secondary outcomes, we will test each secondary outcome at alpha = 0.008 two-tailed to control for multiple comparisons.

For studies involving treatment or diagnosis, provide information about standard of care at Partners (e.g., BWH, MGH) and indicate how the study procedures differ from standard care. Provide information on available alternative treatments, procedures, or methods of diagnosis.

Not applicable

Describe how risks to subjects are minimized, for example, by using procedures which are consistent with sound research design and which do not unnecessarily expose subjects to risk or by using procedures already being performed on the subject for diagnostic or treatment purposes.

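### The two randomisation strata appear in no stated analysis: a small, conditional loss of precision that is almost free to avoid, not a validity error

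*Combined protocol and SAP*

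**What the plan says.** Under Research Design and Methods, the combined protocol and SAP states: "To limit chance confounding between variables that might influence guideline compliance, we will stratify randomization based on two variables (six strata". The factors are travel time to the physician (three bands) and public or private primary insurance. Both are collected in the Baseline Assessment, before randomisation. On allocation, the text says only "after which we will randomize the participant 1:1 to either the Intervention or Control arm (Appendix D"; that appendix is not part of the text available for review.

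The Data Analysis Plan sets the target: "Our primary analysis will compare the mean number of caregiver-reported evaluations completed within 7 months of the index PCP visit". The model is described as "We will analyze the data using a generalized linear model assuming beta-binomial distributed counts of evaluations among those indicated". No covariate or stratum term is named and the link function is not stated. A second test follows: "We will confirm our inference using a permutation test by direct randomization of assigned treatment labels". The two are tied together: "A significant effect of the intervention will be declared only if the permutation test concurs with inference from the beta-binomial regression". The primary test is two-tailed at 0.05.

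On adjustment, Research Design and Methods says that "by not conditioning on PCP characteristics, findings from our primary analysis will be most broadly generalizable", and then that "we do want to increase precision in our secondary analyses by accounting for relevant sources of variation among PCP practices". The covariates listed for that purpose are four PCP-reported variables: practice size, health-centre status, years in practice and number of patients with Down syndrome. Neither stratification factor is among them. The repeated-measures ANOVA and the Wilcoxon tests for the secondary outcomes do not mention the strata either.

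**The concern.** The two factors are judged important enough to shape the allocation, yet they drop out of every stated analysis without a reason. The rationale for an unconditioned primary analysis does not reach them: travel time and insurance are reported by the caregiver at baseline and are not PCP characteristics.

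If the strata are prognostic and balanced by design, a test that ignores them uses a standard error that is too large, so it is slightly conservative. If allocation within strata is not blocked, the unadjusted estimate simply carries avoidable variance. Either way, some power is given up.

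The concurrence rule adds a feature particular to this plan. An effect is declared only when both tests agree, so joint power cannot exceed that of the weaker test. Adjusting the model while permuting an unadjusted statistic would leave the second test as the limit.

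**Working it through.** The plan states no power, effect size, adherence rate or prognostic data, so there is no figure of its own to reproduce. R² is therefore an assumption, shown over a range.

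**Inputs from the document:** N = 200, 1:1 allocation, 3 × 2 = 6 strata, two-tailed alpha 0.05 (critical value 1.96), both tests required. **Assumed:** R² of 0, 2, 5 and 10%, and an effect that gives the adjusted test 80% power, so d = 1.96 + 0.84 = 2.80.

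**Formulas** (Normal approximation, adjusted standard error set to 1)

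- Balanced strata: the unadjusted test in effect rejects when |Z| > 1.96/√(1 − R²). Size = 2[1 − Φ(1.96/√(1 − R²))]; power = Φ(d − 1.96/√(1 − R²)).
- No blocking within strata: power = Φ(d√(1 − R²) − 1.96), and size stays nominal.

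For example, at R² = 5% with balance: 1.96/√0.95 = 2.011; size = 4.4%; power = Φ(2.802 − 2.011) = 78.5%, a loss of 1.5 points.

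| R² | Size, balanced | Points lost, balanced | Points lost, no blocking |
|---|---|---|---|
| 0 | 5.0% | 0 | 0 |
| 2% | 4.8% | 0.6 | 0.8 |
| 5% | 4.4% | 1.5 | 2.0 |
| 10% | 3.9% | 3.1 | 4.3 |

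Against 90% adjusted power, the balanced losses at 5% and 10% are 0.9 and 2.0 points.

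**How demanding are these R² values?** Assume mean adherence 45%, intraclass correlation 0.15 and 3 indicated evaluations. The SD of the proportion completed is √(0.45 × 0.55/3 × (1 + 2 × 0.15)) = 0.327. If a 50/50 insurance split alone carried the effect, the gap needed is 2√R² × 0.327: 9.3, 14.6 and 20.7 points for R² of 2, 5 and 10%. With both factors sharing the effect, 10% still needs about 17 points for insurance and 21 to 25 points between the shortest and longest travel times. So 10% is an upper-end case.

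**Simulation of the joint rule** (beta-binomial data; assumed travel shares 70/22/8%, insurance 50/50, odds ratio 1.67; 3,000 replicates for power). The gain from stratifying both tests, with blocks of 4, was −0.1 points (SE 0.24) at R² = 0, 0.6 (0.27) at 2%, 1.6 (0.31) at 5% and 3.9 (0.41) at 10%. With no blocking it was 1.8 (0.50) at 5% and 5.1 (0.60) at 10%. Joint type I error at R² = 10%, blocks of 4, was 3.9% unadjusted and 5.0% stratified (SE 0.28).

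**Statistic or shuffle?** A simpler Normal-outcome simulation separated the two (N = 200, R² = 10%, 4,000 replicates, 499 permutations, SE about 0.6 to 0.7 points). Joint power:

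| Model / permutation test | Blocks of 4 | No blocking |
|---|---|---|
| Unadjusted / free shuffle, unadjusted statistic | 76.7% | 75.3% |
| Adjusted / free shuffle, unadjusted statistic | 76.9% | 74.0% |
| Adjusted / free shuffle, adjusted statistic | 80.0% | 79.1% |

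Null rejection in the last row was 4.8% and 5.0%. A second Normal-outcome check, also at R² = 10%, compared the adjusted model with a free shuffle of the adjusted statistic against a stratified replay: 85.3% against 85.1% with blocks of 4, and 81.8% against 81.8% with none. A free shuffle of the unadjusted statistic gave 83.5% and 76.6%. Using the adjusted statistic recovers the power; once it is used, the shuffle scheme makes no material difference.

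**The case against.** The strongest reply is that an unadjusted comparison of means after stratified randomisation is a legitimate and, if anything, conservative choice. The plan claims no power figure, so none is missed. If the effect is instead fixed to give 80% power at R² = 0, the unadjusted test has 80.2% to 81.3% power for R² of 2 to 10%: what is lost is a gain never claimed. Every magnitude above rests on assumed values. All of this stands, and it is why the point is low priority. It does not explain why the two factors were left out.

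A second reply is that direct randomisation of labels may already mean re-running the stratified allocation. The wording allows that, so the permutation text is an ambiguity to clear up and not a demonstrated mismatch. Even on that reading, the model without stratum terms caps the joint rule. In the beta-binomial simulation with blocks of 4, the unadjusted model alone had 74.6% and 71.5% power at R² of 5% and 10%, against 75.0% and 74.0% for the joint rule with both tests stratified. At least 0.4 and 2.5 points would still be lost.

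Three stronger readings are tempting and are not supported.

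- That ignoring the strata invalidates the test: its size is at or below nominal throughout.
- That shuffling labels freely itself forfeits the gain: the comparison above shows that the unadjusted statistic is the cause.
- That the gain is the same whatever the block size: that some gain exists does not depend on blocking, but its size does (3.1 against 4.3 points analytically, 3.9 against 5.1 in simulation, at R² = 10%).

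**Conclusion.** The omission is real: two factors chosen for their possible influence on the outcome enter no stated analysis, and the only stated reason for not conditioning does not cover them. The consequence is a conditional loss of precision. It is nil if the strata are not prognostic, up to about 2 points of power for R² of 5% or less, and about 3 to 4 points analytically at an upper-end 10%. These figures assume 80% adjusted power and an R² that the documents do not give; a stronger association would cost more. Where the value falls between the balanced and unblocked figures turns on the block size, which the available text does not show. Type I error is not inflated, and a significant unadjusted result would stand. This is an inexpensive improvement of low priority, not a correction of an error.

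**What to change.** State in the Data Analysis Plan that:

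1. Travel time (three levels) and insurance (two levels) enter the primary beta-binomial model as main effects. This adds 2 + 1 = 3 parameters and avoids six cell terms, since some strata may be small.
2. The confirmatory permutation test uses the same stratum-adjusted statistic. Otherwise the concurrence rule limits power to that of the unadjusted permutation test.
3. Labels are re-randomised by replaying the stratified allocation. This is for exactness under the design, not for power.
4. The difference in mean number of evaluations is reported standardised over the strata, with its interval method named. The plan frames the comparison as one of means, whereas a logit link, if used, would give an odds ratio conditional on the strata.

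The cost is a few sentences and a few lines of code, and no new data, because both variables are recorded before randomisation. If the strata prove unrelated to adherence, the simulated change in joint power is −0.1 points (SE 0.24), which cannot be told from zero. If the sponsor prefers to keep the unadjusted analysis, one sentence giving the reason and specifying the permutation scheme and statistic would close the gap in the text.

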**PARTNERS HUMAN RESEARCH COMMITTEE
PROTOCOL SUMMARY**

Answer all questions accurately and completely in order to provide the PHRC with the relevant information to assess the risk-benefit ratio for the study. Do not leave sections blank.

PRINCIPAL/OVERALL INVESTIGATOR

[name]., M.P.P.

PROTOCOL TITLE

Down Syndrome Clinic to You (DSC2U)

FUNDING

PATIENT-CENTERED OUTCOMES RESEARCH INSTITUTE

VERSION DATE

February 28, 2017

SPECIFIC AIMS

Concisely state the objectives of the study and the hypothesis being tested.

Our core objective is to leverage an innovative technology from Massachusetts General Hospital (MGH), which engages parents/caregivers, so that we can begin to reduce specific health care disparities experienced by those underserved patients with Down syndrome (DS). Specifically, through a randomized control trial (RCT), we will test whether patient/caregiver-initiated online reports with personalized recommendations versus usual care will increase caregiver-reported, provider-driven health actions consistent with national DS guidelines. While all patients with DS have a disparity as defined by their disability, we also intend to mitigate the compounding disparities of geographic location, race/ethnicity, and socioeconomic factors for the majority of families and overcome the limited reach of DS specialty care by taking advantage of the broader reach of the Internet.

BACKGROUND AND SIGNIFICANCE

Provide a brief paragraph summarizing prior experience important for understanding the proposed study and procedures.

Down syndrome (DS) is a rare, chronically debilitating genetic condition caused by extra genetic material from chromosome 21. Patients with DS are prone to multiple chronic conditions over their lifetime, including congenital heart disease, thyroid conditions, gastrointestinal disorders, leukemia, obstructive sleep apnea, and accelerated aging, among others. Most patients with DS have their medical care managed by their primary care providers (PCPs), but a recent study showed that <10% of children and adolescents with DS are up-to-date on even the basic recommendations, such as thyroid screens, celiac testing, audiograms, eye exams, and sleep apnea testing.

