- PCP practicing in a federally qualified community health center: yes or no (collected in PCP Experience Survey during Post-visit Assessment 1)
- Years of PCP practice (collected in PCP Experience Survey during Post-visit Assessment 1)
- Number of patients with Down syndrome cared for by PCP (collected in PCP Experience Survey during Post-visit Assessment 1)

Baseline Assessment (Intervention & Control Arms)

The intervention and control groups will both complete a Baseline Assessment; up to 3 e-mail reminders will be sent to the parent/caregiver every 1 week. The Baseline Assessment, implemented using REDCap (Research Electronic Data Capture), a secure, NIH-funded, and Health Insurance Portability and Accountability Act (HIPAA) compliant web-based application hosted by Partners HealthCare Research Computing, will request the following information:

- *Caregiver information*: first name, last name, gender, date of birth, relationship to patient, phone number, address, and email address
- *Child or dependent's information*: first name, last name, gender, date of birth, race/ethnicity (NIH standardized format)
- *PCP information*: first name, last name, gender, office phone, office address and e-mail (if available)
- Travel time to primary care physician: < 30 minutes; 30–60 minutes; > 60 minutes
- Primary insurance: public (e.g., Medicaid, Medicare) or private
- *Date of annual well visit ("PCP visit") appointment*
- *Symptoms indicating need for celiac disease testing or sleep study*. We plan to assess these symptoms among other symptoms not related to these conditions so as to minimize any priming effects. For example, "Does your child snore at night?" might be asked next to "Does your child have any rashes?" (A sleep study might be warranted for snoring, but not for rashes.) ([Appendix E](#))
- *Health Care Outcome Survey* (Metrics measuring adherence to national health care guidelines): thyroid screening, celiac disease screening, sleep apnea testing, ophthalmology exams, and audiograms ([Appendix F](#))

- *Secondary outcome measures:* PedsQL 2.0 Family Impact Module and PedsQL 4.0 parent-proxy, standard Short Form 15 Generic Core Scales (Appendix G)

Intervention Arm

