- Parent/Caregiver Experience Survey (for Secondary Outcomes) (Appendix K)
- Primary Care Provider Experience Survey (for Secondary Outcomes) (Appendix L)

Survey Implementation

The Experience Surveys (for both the parents/caregivers and PCPs) will be administered approximately 2 weeks after the PCP visit at Post-visit Assessment 1 (T1) (Figure 1). Parents/Caregivers will be invited by e-mail to complete their experience survey through REDCap. PCPs will receive their experience survey by mail, with an option to complete the survey electronically on REDCap. PCPs whose e-mails were provided by the parents/caregivers will also receive a direct invitation by e-mail to complete their survey. In order to minimize loss to follow-up, reminder e-mails will be sent 3 times about 2 weeks apart, concluding with a phone call in the eighth week by our study personnel. We certainly hope to maximize the PCP response rate, but our primary outcomes are not dependent on their responses.

Parents/Caregivers will be asked by e-mail to complete the Health Care Outcomes Survey through REDCap approximately seven months after the PCP visit at Post-visit Assessment 2 (T2) (Figure 1). In order to minimize loss to follow-up, reminder e-mails will be sent 3 times about every 2 weeks apart, concluding with a phone call in the 8th week by our study personnel.

[figure not shown]

Figure 1. Survey implementation at various points.

- **Baseline:** Health Care Outcome Survey, PedsQL 2.0 Family Impact Module and PedsQL 4.0 parent-proxy, standard Short Form 15 Generic Core Scales
- **T₀ (PCP Visit)**
- **T₁ (Post-visit Assessment 1):** PedsQL 2.0 Family Impact Module and PedsQL 4.0 parent-proxy, standard Short Form 15 Generic Core Scales, Parent/Caregiver Experience Survey, and PCP Experience Survey
- **T₂ (Post-visit Assessment 2):** Health Care Outcome Survey, PedsQL 2.0 Family Impact Module and PedsQL 4.0 parent-proxy, standard Short Form 15 Generic Core Scales

Validation Assessment

Ten percent of the respondents across both groups will be asked to validate their self-report by providing documentation of laboratory and procedural results. For example, if parents attest to thyroid checks being done for their

sons/daughters, they will be asked to send documentation of the primary outcomes (e.g. study report or physician sign off). These participants will also receive 3 reminder e-mails and a phone call every 2 weeks.

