If discrepancies are identified between parental report and source verification in more than 10% of these samples, then our team will perform a full verification of all 200 participants. Verification will be made by source documentation (e.g., sleep study reports) or verbal confirmation through telephone calls to primary care physicians.

Primary Outcomes:

We will be measuring adherence to detect improvement in: thyroid screening, celiac disease screening, sleep apnea testing, ophthalmology exams, and audiograms

- *Thyroid*: TSH should be checked annually beginning at age 1
- *Celiac disease*: if symptoms present, obtain tTG-IgA and total IgA annually
- *Sleep study*: performed by 4 years of age and, again, if symptomatic
- *Ophthalmology exam*: annually, ages 1-5; every 2 years, ages 5-13; every 3 years, ages 13-21; every 2 years, ages 21 and older
- *Audiograms*: annually up to age 21, every 2 years thereafter

The indication for 1, 2, 3, 4, or 5 evaluations for a given participant at the time of their PCP visit based on age, history, and symptoms will be collected prior to randomization as described in the "Baseline Assessment" section.

Secondary Outcomes:

We also want to determine whether the intervention improves quality of life as measured by the nationally validated PedsQL survey instruments.

Six summary scores will be derived from the two PedsQL instruments: measures of (1) psychosocial health, (2) physical health, and (3) an overall total score from the PedsQL 4.0 parent-proxy, standard Short Form 15 Generic Core Scales; and measures of (4) parental health-related quality of life, (5) family functioning, and an (6) overall total score from the PedsQL 2.0 Family Impact Module.

We will also measure the quality of experience with the intervention from parents and PCPs and identify ways that the *Caregiver Checklist* and *Primary Care Provider Plan* could best serve the needs of underserved patients with DS. For this assessment, rather than assuming we know which questions to ask to best assess their experience, we will engage our Parent/Caregiver and PCP WGs to help us pose relevant questions. Our expectation is that the assessments will ask for their level of satisfaction with the content and

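### A cheap precision gain is left open: the primary model and its permutation test name no covariate, although adherence on the same five evaluations is recorded before randomisation

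*Combined protocol and SAP*

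**What the plan says.** All references are to the combined protocol and SAP.

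- **Primary analysis (Data Analysis Plan).** "We will analyze the data using a generalized linear model assuming beta-binomial distributed counts of evaluations among those indicated with parameters estimated by maximum likelihood". The comparison is of the mean number of evaluations completed within 7 months of the index visit, two-tailed at 0.05. A permutation test of the treatment labels must agree before an effect is declared. No covariate is named for either test.
- **Baseline measure (Baseline Assessment).** The Health Care Outcome Survey is described as "Metrics measuring adherence to national health care guidelines): thyroid screening, celiac disease screening, sleep apnea testing, ophthalmology exams, and audiograms". These are the five evaluations of the primary outcome. The key to Figure 1 gives the same list of instruments at baseline and at T2: "Health Care Outcome Survey, PedsQL 2.0 Family Impact Module and PedsQL 4.0 parent-proxy, standard Short Form 15 Generic Core Scales".
- **Timing (study procedures).** Consent and the baseline assessment come first: "Our study personnel will then be notified by e-mail, after which we will randomize the participant 1:1". The stratification factors come from the same assessment: "we will stratify randomization based on two variables (six strata) collected prior to randomization during the Baseline assessment".
- **Stated reason for not conditioning (study procedures).** "Moreover, by not conditioning on PCP characteristics, findings from our primary analysis will be most broadly generalizable". This concerns characteristics of the primary care provider (PCP) only. Those are kept as covariates for secondary analyses, where more precision is the stated aim.
- **Baseline information already used (Primary Outcomes).** The indication for one to five evaluations "at the time of their PCP visit based on age, history, and symptoms will be collected prior to randomization".

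**The concern.** A pre-randomisation measure of the outcome itself is often among the better candidates for a prognostic covariate. Here it is already planned for collection, and the plan uses baseline values for the secondary PedsQL outcomes through a shared-baseline model. The primary outcome has no matching provision. The reason given for leaving PCP characteristics out does not reach a caregiver-reported baseline measure.

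What is at stake is precision, not validity. If families with good past adherence are also more likely to complete what is now due, adjustment would remove some between-participant variation from the treatment comparison. With 200 participants and a rule that needs two tests to agree, that may be worth having. If past adherence does not predict completion, adjustment costs a little power.

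**Working it through.** **Inputs from the documents.** N = 200, allocated 1:1 (100 per arm); two-sided alpha 0.05; six randomisation strata. The plan states no power, effect size, standard deviation or control rate, so there is no figure of its own to reproduce.

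**Assumed.** Unadjusted power of 80%, and r from 0 to 0.4. Here r is the correlation between the baseline covariate and completion of the indicated evaluations.

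**Step 1: does the number indicated already do this work?** In the planned model the count for participant i is beta-binomial with m_i trials and mean m_i × mu_i, where logit(mu_i) = a + b × treatment. The number indicated, m_i, scales the expected count. It does not enter mu_i, the probability that an indicated evaluation is completed. History can therefore shape m_i without being used to predict completion.

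**Step 2: size of the gain.** In a linear model, adjusted variance = (1 − r²) × unadjusted variance. For 80% power the standardised effect is 1.960 + 0.842 = 2.802, so

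power = Φ(2.802/√(1 − r²) − 1.960), and equivalent unadjusted N = 200/(1 − r²).

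| r | Variance removed | 2.802/√(1 − r²) | Power | Equivalent N |
|---|---|---|---|---|
| 0 | 0% | 2.802 | 80.0% | 200 |
| 0.1 | 1% | 2.816 | 80.4% | 202 |
| 0.2 | 4% | 2.859 | 81.6% | 208 |
| 0.3 | 9% | 2.937 | 83.6% | 220 |
| 0.4 | 16% | 3.057 | 86.4% | 238 |

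**Step 3: cost if the covariate is useless.** With two extra parameters (the covariate and a missing-data indicator), variance is multiplied by about 1 + 2/195. Power = Φ(2.802/√(1 + 2/195) − 1.960) = Φ(0.827) = 79.6%, a loss of 0.4 points.

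**Step 4: check by simulation of the two-test rule.** There were 1,500 paired replicates per setting with N = 200, and history set the number indicated. Strata shares, applicability of each item, overdispersion, missingness and effect were all assumed. The entries are joint-rule power, unadjusted to adjusted, in percent; the Monte Carlo error of each change is 0.5 to 0.8 points.

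| Baseline items up to date | r = 0 | 0.1 | 0.2 | 0.3 | 0.4 |
|---|---|---|---|---|---|
| 10%, only overdue items indicated | 75.3–74.5 | 75.2–74.6 | 75.9–77.5 | 78.2–80.2 | 74.9–79.5 |
| 40%, only overdue items indicated | 76.9–75.7 | 75.8–75.8 | 76.4–78.3 | 78.2–80.6 | 77.3–83.0 |
| 40%, half of current items due again | 75.3–74.4 | 74.7–74.8 | 74.8–76.3 | 74.9–79.0 | 77.9–83.3 |

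The loss at r = 0 is about 1 point and break-even is near r = 0.1. The gain is 2.0 to 4.1 points at r = 0.3 and 4.6 to 5.7 at r = 0.4. Joint-rule type I error, checked in the second setting at r = 0.3, was 4.3% unadjusted and 4.5% adjusted (standard error 0.4).

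A separate simulation, in which the number indicated did not depend on the covariate, gave power of 74% falling to 73% with no prognostic value, 65% rising to 72% at r of about 0.28, and 59% rising to 71% at r of about 0.43 (Monte Carlo error about 2 points). The direction agrees. The size depends on inputs that the documents do not supply.

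**The case against.** **Nothing needs mending.** A randomised two-arm comparison with a permutation check is valid without covariates, and the plan is a brief protocol summary that neither lists nor excludes them. This stands. A reader might infer that the unadjusted analysis is biased, or that the plan rules adjustment out. The documents support neither: the covariate's absence rests on silence.

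**Baseline history is already used.** It helps set the number indicated. If only overdue items count as indicated, the proportion up to date is itself built from that number. This stands in part. It would be wrong to say that the baseline survey goes unused, and the remaining r may be low. But the number indicated enters as the number of trials, not as a predictor of completion, so the objection does not remove the point.

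**The gain cannot be sized and may be negative.** This stands. Below r of about 0.1 there is nothing to gain, and at 0.3 the gain is still modest.

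**The background adherence figure does not rescue the sizing.** The Background says "a recent study showed that <10% of children and adolescents with DS are up-to-date on even the basic recommendations". A reader might take this as joint adherence on five items, infer a per-item rate of 0.10^(1/5) = 63%, and expect a wide-ranging covariate with a large gain. That step needs all five items to apply and to be independent within a person, and independence would remove the very trait that the covariate is meant to capture. Under the simulation's between-person logit SD of 1.0 and its item applicability, 63% per item would put about 25% of people up to date on everything applicable, against the stated figure of under 10%; about 44% per item would match it. The figure also concerns children and adolescents, whereas the trial takes all ages.

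**Conclusion.** The point holds as an optional improvement of low severity. The primary analysis is valid as written, but it leaves out, as a predictor, a pre-randomisation measure of the same five evaluations, and the plan's stated reason for not conditioning does not cover that measure.

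The gain is small below r of about 0.3, modest at 0.3 (3.6 points by formula, equivalent to about 20 more participants) and material from about 0.4 (6.4 points, about 38 more). The possible loss is about 0.4 to 1 point. These sizes rest on an assumed 80% unadjusted power, on a variance relation for linear models applied to a beta-binomial, and on an r that the documents do not give. A large gain should not be inferred. A sponsor who expects a low r may reasonably decline, and it would help to record that choice before unblinding.

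**What to change.** Before unblinded data are seen, pre-specify the following.

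1. **Covariate.** Add baseline adherence from the Health Care Outcome Survey to the beta-binomial model: the proportion of applicable evaluations up to date or, if the items do not allow this, a simple baseline count. Use one indicator category for participants with missing baseline items or none applicable.
2. **Permutation test.** Base it on the covariate-adjusted treatment statistic, and permute labels within the six randomisation strata.
3. **Estimate.** Report the covariate-standardised difference in mean evaluations completed. With a logit link, adjustment turns the treatment coefficient into a conditional odds ratio; standardising keeps the estimate aligned with the planned comparison of means.
4. **Sensitivity.** Keep the unadjusted analysis.

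**Cost.** About 0.4 to 1 point of power if the covariate is uninformative, plus analysis work: one covariate and an indicator, a standard error for the standardised difference, and an adjusted, stratified permutation routine. No new data collection is needed. The survey itself (Appendix F) is not among the pages available, so the sponsor should check whether its items can establish up-to-date status under the different intervals listed under Primary Outcomes. If they cannot, the simple count applies; the simulation above did not test that version.
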